- Upon arrival at the Center for Exercise Science for a scheduled visit, participants will be screened for history and symptoms of COVID-19 and body temperature will be taken using a contactless forehead thermometer prior to exiting their car. If they answer yes to any of the screening questions and/or their temperature is greater than 100.4 degrees, then they will need to reschedule the visit. Participants will be given a surgical mask and a 2 oz. bottle of hand sanitizer. They will be asked to wear the mask and use the hand sanitizer prior to entering the building and frequently sanitize their hands during the visit and social distance whenever possible.
- During the pandemic, participants will complete a COVID-19 test 3-5 days prior to VO₂max testing and only those who are confirmed negative will proceed to complete the VO₂max test. The COVID-19 test will be prescribed as long as [name] deems it necessary and will be paid by the study.
- Exercise sessions will be performed at home and exercise supervision will be conducted remotely live via UF Zoom using a wearable device which provides real-time heart rate monitoring.

Specific risks associated with nitroglycerin: Risks related to nitroglycerin administration will be minimized by providing adequate clinical supervision and by taking the following safety precautions. An intravenous catheter will be inserted in a peripheral vein prior to nitroglycerin administration, in case the effect of nitroglycerin necessitates the administration of fluids or medication. ECG will be monitored continuously. Blood pressure will be monitored prior to nitroglycerin administration and post-administration as frequently as deemed necessary. For individuals whose systolic blood pressure is <100 mmHg, nitroglycerin will not be administered. Subjects will remain in bed for 30 minutes after nitroglycerin administration to allow blood pressure to return to baseline before ambulating. Nitroglycerin has been administered safely in our laboratory for more than 10 years, and in other laboratories, and clinical situations worldwide.

Risks associated with intra-arterial catheter and cell collection: Risks related to intra-arterial catheter insertion and cell collection will be minimized by having an experienced clinician from the Pulmonary and Critical Care Division, [name], perform the procedure. [name] will use ultrasound imaging to guide the cannulation to avoid injury to nerves and surrounding structures. Subjects will be screened for contraindications including absent pulse at the location of the artery, history of Raynaud's Syndrome, insufficient collateral perfusion based on Allen test, coagulopathy, recent use of thrombolytic, anticoagulant or antiplatelet drugs, and partial or full thickness burns over the proposed cannulation site. Up to two attempts to insert the arterial catheter will be performed; attempts will be aborted if any complications are expected. [name] will monitor the patient until the arterial line procedure and cell collection are completed and no complications are noted.

Specific risks and complications will be mitigated and managed as follows:

- a. Radial Artery Spasm (RAS)
 - i. Subjects will be monitored for RAS clinically by physician inserting arterial catheter
 - ii. Initial management:
 1. Subjects scheduled to receive nitroglycerin 0.4 mg sublingual (as per study protocol to assess endothelium-independent dilation) will receive the dose of nitroglycerin as per study protocol and RAS will be reevaluated (at 10-min intervals up to 30 min). If no improvement, then escalation to higher level of care will be initiated.
 2. Subjects not scheduled to receive nitroglycerin will be monitored for severity of RAS. If moderate or severe by clinical judgement, then the patient will receive a single dose of nitroglycerin 0.4 mg sublingual and RAS will be reevaluated (at 10-min intervals up to 30 min). If no improvement, then escalation to higher level of care will be initiated.
- b. Thrombosis
 - i. Mitigation of risk:
 1. Cancel procedure if subject has history (or present during evaluation) of Raynaud's phenomenon
 2. Catheter will stay inserted for less than 5 min
 3. No use of large bore catheters, only 20G or smaller

4. No insertion if patient has low cardiac output (by history)
5. No insertion if patient has history of severe peripheral artery disease
6. No insertion if blood vessel is considered too small for cannulation

- ii. Initial management: If moderate or severe by clinical judgement, then the patient will receive a single dose of nitroglycerin 0.4 mg sublingual and RAS associated with thrombosis will be reevaluated (at 10-min intervals up to 30 min). If no improvement, then escalation to higher level of care will be initiated.

- c. Dissection, pseudoaneurysm, AV fistula
 - i. Mitigation of risk by using procedures described above and
 1. Continuous clinical monitoring at 10-min intervals up to 30 min.
 2. Local pressure to control bleeding and hematoma
 3. If present and no improvement with initial local pressure, then escalation to higher level of care will be initiated.
- d. Infection
 - i. Mitigation of risk:
 1. All sterile insertion as per usual guidelines. Use of mask, caps, gowns, sterile gloves, and chlorhexidine (or equivalent if patient allergic) to prepare the skin.
 2. Catheter will be inserted for less than 5 minutes.
- e. Blood loss
 - i. Mitigation of risk:
 1. No arterial puncture will be attempted in any subject with systemic anticoagulation.
 - ii. Initial management:
 1. Bleeding will be controlled by local pressure; monitoring at 5, 10, and 15 min after removal of arterial catheter. If bleeding persists continuous pressure and evaluation at 10-minute intervals up to 30 min.
 2. If bleeding present and no improvement with initial local pressure, then escalation to higher level of care will be initiated.
- f. Neuropathy
 - i. Mitigation of risk:
 1. Use of ultrasound guided technique to avoid nerve injury.
 2. Abort procedure if producing pain or neurological injury.
 - ii. Initial management:
 1. If severe neurological injury noticed, then escalation to higher level of care will be initiated.

Procedure for escalation of care after initial control in research laboratory:

Local initial first aid, including pressure to stop bleeding and vital signs monitoring. The patient will be transferred to University of Florida Hospital for further evaluation and care if complications arise. If emergent we will contact 911 for immediate support and transport. We will immediately refer patient to University of Florida/Shands Medical Center for any complications for further evaluation and therapy.

Risks associated with exercise training:

In general, risks related to exercise training will be minimized by:

- adhering to the exercise training guidelines published by the American Heart Association and the American College of Sports Medicine
- providing thorough health screening to ensure there are no contraindications for exercise training
- providing remote live supervision of exercise training via Zoom

Minimizing specific risks associated with exercise training:

Cardiac risks during exercise will be minimized by completing extensive health screening tests before subject enrollment to the exercise intervention. Subjects with signs of cardiovascular disease or those at elevated risk for cardiac complications will be excluded from the study (see exclusion criteria). A physical examination will be conducted, and medical history and resting ECG will be reviewed for contraindications to exercise. Prior to exercise testing, heart rate and blood pressure will be obtained while the subjects rest supine, sitting and standing to screen for cardiac autonomic dysfunction. Baseline maximal exercise tests will be performed to rule out the presence of silent myocardial ischemia. Because the exercise level during the diagnostic tests will be maximal, it should allow identification/exclusion of individuals who are likely to develop ischemia during the exercise training. In addition, subjects will be educated on how to recognize cardiovascular disease symptoms such as angina, dizziness and excessive shortness of breath. They will be asked to inform the research team immediately if they experience any of these symptoms during the diagnostic exercise test or the exercise sessions. If participants experience a medical emergency during an exercise session, we will call 911 while we continue to monitor them via video conferencing. In summary, cardiac risks associated with exercise training will be minimized, although we recognize they cannot be completely eliminated. Overall, the widely accepted benefits of exercising in older adults should outweigh the risks.

8. Possible Benefits

The risk-to-benefit ratio is relatively small because the risks of participating in this study are relatively small. Subjects may or may not benefit from participating in this research study. The subjects will receive information regarding their health at no cost from the extensive testing performed for screening purposes (i.e., medical information derived from physical examination, diagnostic exercise test, blood pressure measurements, body composition analysis including bone density, aerobic fitness, physical activity and dietary analysis, and general blood tests including comprehensive metabolic panel, lipid panel, insulin, complete blood count with differential). Although individual responses may vary, exercise training has been shown to lead to many health benefits that may improve quality of life or lower the risk for heart disease including higher fitness level, improved heart function, healthier blood vessels, lower blood pressure, lower body fat and blood lipids, reduced stress and depression. Participation in the proposed studies could also contribute to the advancement

of scientific information that may have important implications for exercise prescription for preventing cardiovascular disease in aging. The study will use a translational research approach to gain mechanistic insight, for the first time, into sex differences in *in vivo* systemic/cellular/molecular adaptations to exercise in older adults.

9. Conflict of Interest

There is no conflict of interest to report.

LITERATURE CITED

1. Bonetti PO, Lerman LO and Lerman A. Endothelial dysfunction: a marker of atherosclerotic risk. *Arteriosclerosis, Thrombosis & Vascular Biology*. 2003;23:168-75.
2. Cai H and Harrison DG. Endothelial dysfunction in cardiovascular diseases: the role of oxidant stress. *Circulation Research*. 2000;87:840-4.
4. Inaba Y, Chen JA and Bergmann SR. Prediction of future cardiovascular outcomes by flow-mediated vasodilatation of brachial artery: a meta-analysis. *The international journal of cardiovascular imaging*. 2010;26:631-40.

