[figure not shown]
Our overarching hypothesis is that acute and chronic endothelial responsiveness to aerobic exercise is influenced by sex in healthy aging and acute endothelial responses will be predictive of chronic endothelial adaptations. Our experimental model of acute and chronic responses to NWA-HIIT presents a unique tool to test this hypothesis and explore the underlying mechanisms in healthy sedentary older adults. *Our translational approach will examine, for the first time, sex differences in endothelial responses to exercise at multiple levels spanning from the molecular and cellular to the organism level. Identifying the defective adaptive pathways in women may lead to novel therapeutic targets.*

5. Specific Aims

1. To study sex differences in chronic endothelial adaptations to aerobic exercise
2. To study sex differences in acute endothelial responses to aerobic exercise and if acute endothelial responses are predictive of chronic endothelial adaptations.

6. Research Plan

Study design and timing of measures. An equal number of older men and postmenopausal women will be enrolled in this study and the same subjects will complete Aims 1 and 2. For Aim 1, subjects will complete 8-week NWA-HIIT preceded by an 8-week control period of normal lifestyle. Therefore, each subject will serve as his/her own control and the control period of normal lifestyle will also allow determination of potential changes due to measurement error. FMD and other measures associated with Aim 1 will be assessed at baseline, and after the 8-week control and 8-week NWA-HIIT (**Diagram 1**). FMD and other measures associated with Aim 2 will be assessed at pre-exercise, at the end of a single session of NWA-HIIT, and 1-hr and 24-hrs post-exercise (**Diagram 2**) in the untrained and trained state (**Diagram 1**). Measures in the trained state for Aim 2 will be completed 72-96 hours after the last chronic exercise session.

Study procedures will be performed at the Integrative Cardiovascular Physiology Laboratory, Center for Exercise Science, University of Florida.

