Sample Size, Statistical Analyses, and Anticipated Results

Sample size justification. For power analyses, we set $\alpha=0.05$ and $\beta=0.80$ and used the smallest effect size (ES) based on our preliminary data on FMD, which is our primary outcome. To detect significant sex differences in acute/chronic FMD responses, we will need 11 men and 11 women (ES=1.57 for acute and 1.28 for chronic response). To detect

significant acute and chronic changes in FMD in response to NWA-HIIT in older men we will need 10 men (ES=1.02 for acute and 3.87 for chronic response). We anticipate we will need to consent and screen 165 research participants to meet the study inclusion criteria and obtain complete datasets in 11 men and 11 women.

Statistical analyses. Our primary outcome will be FMD. For both Aim 1 and 2, we will use mixed factorial ANOVA. Post hoc and multiple tests will be corrected using the Bonferroni adjustment. Secondary analyses will be performed using ANCOVA to account for influence of potential confounders. Exploratory analysis will evaluate the mechanisms by which exercise influences FMD and stimulate future mechanistic studies. Using linear regression, we will examine whether responses to acute NWA-HIIT are correlated with responses to chronic 8-week NWA-HIIT. Analysis of the RNA sequencing data will be conducted by the ICBR bioinformatics staff.

HUMAN SUBJECTS

Human Subject Characteristics

Subjects will be sedentary men and postmenopausal women recruited from the community using advertisements. Subjects will be screened by our experienced study clinicians with oversight by our cardiologist ([name]) according to the study inclusion/exclusion criteria based on the medical history, physical examination, general blood tests and diagnostic maximal exercise test.

Inclusion criteria

- adults able to give consent
- men and women
- women must be postmenopausal (either natural or surgical)
- 60 to 79 years of age

Exclusion criteria

- any relevant cardiovascular diseases (e.g., history of coronary artery bypass surgery or angioplasty, or heart failure, myocardial infarction, angina pectoris, peripheral arterial disease)
- myocardial ischemia during maximal graded exercise test
- major chronic clinical disease (e.g., diabetes, renal or hepatic disease or infection with hepatitis B, C, or HIV)
- seizures, or other relevant on-going or recurrent illness
- recent (within 3 months) or recurrent hospitalizations
- systolic blood pressure <100mmHg

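### The power statement gives beta as 0.80, which means 20% power; the stated sample sizes show that power of 0.80 (beta 0.20) was meant

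*Combined protocol and SAP*

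**What the plan says.** Under Sample Size, Statistical Analyses, and Anticipated Results, the sample size justification sets the error rates and the choice of effect size: "we set $\alpha=0.05$ and $\beta=0.80$ and used the smallest effect size (ES". The effect sizes come from preliminary data on flow-mediated dilation (FMD), the primary outcome. Two sample sizes follow:

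- For the sex difference in FMD response: "we will need 11 men and 11 women (ES=1.57 for acute and 1.28 for chronic response".
- For the change within older men: "we will need 10 men (ES=1.02 for acute and 3.87 for chronic response".

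The recruitment target is to "obtain complete datasets in 11 men and 11 women", so 22 is the number analysed and no dropout inflation applies to it.

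The paragraph does not say whether tests are one-sided or two-sided, and it does not define the effect size. The Statistical analyses paragraph names a mixed factorial ANOVA and adds: "Post hoc and multiple tests will be corrected using the Bonferroni adjustment".

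**The concern.** Alpha and beta are set side by side as error rates. Alpha is the chance of a false positive and beta the chance of a false negative, so power is 1 − beta. With beta at 0.80, power is 1 − 0.80 = 0.20. Read literally, the design would miss a true effect of the assumed size four times in five.

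This is the only statement of power in the plan, so no other sentence corrects it. An ethics committee or statistical reader needs to know what 22 complete datasets deliver. The question has weight because 165 people are to be consented and screened to obtain them, and participants have arterial catheterisation with cell collection at three visits (5, 7 and 10).

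**Working it through.** **Inputs.** All are from the sample size justification unless marked.

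- Alpha 0.05. Two-sided testing is an assumption; one-sided is tried below.
- Sex difference: 11 per sex; effect size (ES) 1.28 chronic and 1.57 acute, read as standardised mean differences.
- Change within men: 10 men; ES 1.02 acute and 3.87 chronic, read as paired standardised changes.
- Equal numbers by sex, from Section 6, study design: "An equal number of older men and postmenopausal women will be enrolled in this study and the same subjects will complete Aims 1 and 2".

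**Formulas.** Exact power uses the noncentral t distribution.

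- Two-sample t-test, n per sex: df = 2n − 2, noncentrality = ES × √(n/2).
- Paired t-test, n men: df = n − 1, noncentrality = ES × √n.
- Power is the probability that |t| exceeds the 97.5% point of the central t with the same df.

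**Step 1: reproduce the stated sizes with power 0.80.** The smallest effect size in each pair drives the result.

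- Sex difference, ES 1.28, n = 11: noncentrality 1.28 × √5.5 = 3.00, df 20, power 0.815. At n = 10 power is 0.772, so 11 is the smallest size reaching 80%.
- Within men, ES 1.02, n = 10: noncentrality 1.02 × √10 = 3.23, df 9, power 0.818. At n = 9 power is 0.764, so 10 is the smallest.

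Both stated sizes are matched exactly. The larger effects need fewer participants: 8 per sex at ES 1.57 and 3 men at ES 3.87.

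**Step 2: apply beta 0.80 literally (power 0.20).**

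- ES 1.28: n = 2 gives 0.123 and n = 3 gives 0.228, so 3 per sex.
- ES 1.02 paired: n = 3 gives 0.184 and n = 4 gives 0.298, so 4 men.

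**Step 3: try other readings.**

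| Sides | Power | Per sex (ES 1.28) | Men (ES 1.02) |
|---|---|---|---|
| Two | 0.20 | 3 | 4 |
| One | 0.20 | 2 | 3 |
| Two | 0.80 | 11 | 10 |
| One | 0.80 | 9 | 8 |
| Two | 0.85 | 13 | 11 |
| One | 0.85 | 10 | 9 |
| Two | 0.90 | 14 | 13 |
| One | 0.90 | 12 | 10 |
| Plan | – | 11 | 10 |

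Only two-sided 80% power matches both figures. One-sided 90% comes close (12 and 10). No 20% reading comes near.

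**Step 4: power at 11 per sex, two-sided, each comparison alone.** Chronic (ES 1.28): 0.815. Acute (ES 1.57): noncentrality 1.57 × √5.5 = 3.68, power 0.938.

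**Step 5: both comparisons together, only if both were required.** The documents give no correlation between the two responses. Under any dependence, joint power is at least 0.938 + 0.815 − 1 = 0.753 and at most the smaller of the two, 0.815. Independence gives 0.938 × 0.815 = 0.764. Simulation, with the correlation aligned to the direction of the effects, gives about 0.77 at 0.3, 0.79 at 0.5 and 0.80 at 0.8.

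**The case against.** The strongest defence is that this is a slip of notation. The intended value can be recovered from the same paragraph, and recruitment, sample size and analysis are unaffected. That stands, and it limits the point to a correction of the text. It does not remove the point, because a reader has to redo the calculation to learn the power.

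Three stronger readings are tempting, and the documents support none of them.

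- **That the trial is underpowered, or planned to miss its effect four times in five.** The stated 11 and 10 rule this out under the plan's own effect sizes.
- **That power for the whole hypothesis is only about 76%.** The overarching hypothesis in Section 4 does name both responses ("acute and chronic endothelial responsiveness to aerobic exercise is influenced by sex in healthy aging"), and multiplying the two powers gives 0.764. But Section 5 lists the chronic and acute questions as separate aims, and no success rule requires both tests to be significant. The product also assumes independence, although the same participants supply both responses and the plan expects them to be related: "acute endothelial responses will be predictive of chronic endothelial adaptations".
- **That 81% and 94% are what the planned analysis will deliver.** They are t-test figures. The plan's analysis is a mixed factorial ANOVA over several time points with Bonferroni correction, and the plan does not say which contrast the effect sizes describe. As an illustration only, splitting alpha over the acute and chronic sex comparisons (0.025 each) would give 0.886 and 0.716; the plan does not say that the correction is applied across them.

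It is also fair to object that two-sided testing is inferred from the match. The sponsor has to confirm it.

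**Conclusion.** The concern holds as a labelling error. The plan's only power figure, read as written, is 20%, while its sample sizes correspond to 80%. The gap is large on both counts: 3 against 11 per sex, and 4 against 10 men. Two separately stated sizes lead to the same explanation, so confidence is high that power of 0.80 was meant. The sample size itself needs no change.

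The conclusion rests on reading the effect sizes as standardised mean differences (between sexes) and paired standardised changes (within men), and on two-sided alpha 0.05. The per-comparison powers of about 81% and 94% depend further on the preliminary effect sizes being true. No joint power claim is warranted from the plan as it stands.

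**What to change.** Replace the error-rate statement in the sample size justification with wording to this effect:

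> Alpha = 0.05 (two-sided; sponsor to confirm), power = 0.80 (beta = 0.20). Under a two-sample t-test at the preliminary effect sizes, 11 per sex gives about 81% power for the chronic and about 94% for the acute sex difference, each taken alone and before any Bonferroni correction.

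If the sponsor intends both sex differences to be required for success, the plan should say so and give joint power as a range of about 75% to 81%, depending on the unstated correlation. Otherwise no joint figure is needed.

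The cost is one or two sentences. Recruitment, visits and analysis stay as they are.

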Cardiovascular disease (CVD) is the leading cause of death in the U.S. in both men and women. Although biological sex is an important determinant of CVD pathophysiology, a major knowledge gap remains regarding sex differences in CVD prevention and treatment. A key early event in CVD development is endothelial dysfunction, characterized by impaired flow-mediated dilation (FMD). Aging progressively impairs endothelial function which independently predicts CVD progression and events. Therefore, strategies to optimize endothelial function in aging are clinically important. Regular aerobic exercise ameliorates endothelial dysfunction in healthy older men, but the data in healthy postmenopausal women are inconsistent with many studies showing no effect. The mechanisms underlying these sex disparities are unknown. Higher intensity exercise is thought to be required for chronic endothelial adaptations in postmenopausal women, but this has not been investigated. We have developed a novel exercise strategy by adapting high-intensity interval training (HIIT) on a non-weight-bearing all-extremity (NWA) ergometer. We have demonstrated that our innovative NWA-HIIT is feasible and safe in older adults. The primary objective of this study is to examine sex differences in acute and chronic endothelial responses to NWA-HIIT in older men vs. postmenopausal women. Our overarching hypothesis is that acute and chronic endothelial responsiveness to aerobic exercise is influenced by sex in healthy aging and acute endothelial responses to exercise will be predictive of chronic endothelial adaptations.

4. Background

Cardiovascular disease (CVD) is the leading cause of death in the U.S. in both men and women. Although biological sex is increasingly recognized as an important determinant of CVD development, progression and outcomes, a major gap remains regarding sex differences in CVD pathophysiology, prevention and treatment. A key early event in CVD development is endothelial dysfunction, characterized by impairments in flow-mediated dilation (FMD)^{1, 2}. In women, the onset of endothelial dysfunction begins a decade later than in men, but the rate of decline is steeper³. Aging progressively impairs endothelial function which independently predicts CVD progression and events⁴. Therefore, strategies to optimize endothelial function in aging are clinically important but should account for the potential impact of sex.

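### The 11 per sex holds only if the chronic FMD sex difference is tested at an undivided 0.05, and the plan does not say whether its Bonferroni rule covers the two contrasts in its primary objective

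*Combined protocol and SAP*

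**What the plan says.** The opening summary gives one primary objective with two parts and does not rank them: "The primary objective of this study is to examine sex differences in acute and chronic endothelial responses to NWA-HIIT". Section 5 lists the chronic question as Aim 1 and the acute question as Aim 2. Section 6 has the same people complete both aims.

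Under Sample size justification, a single alpha serves all calculations: "For power analyses, we set $\alpha=0.05$ and $\beta=0.80" (the 0.80 is evidently meant as power). Both sex contrasts are sized together: "To detect significant sex differences in acute/chronic FMD responses, we will need 11 men and 11 women", with "ES=1.57 for acute and 1.28 for chronic response". The target is to "obtain complete datasets in 11 men and 11 women", so the 22 are completers.

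Under Statistical analyses: "Our primary outcome will be FMD. For both Aim 1 and 2, we will use mixed factorial ANOVA". The only multiplicity rule is "Post hoc and multiple tests will be corrected using the Bonferroni adjustment". The plan gives no testing order, no division of alpha, no definition of the Bonferroni family, and no statement of whether one or both contrasts must be significant.

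**The concern.** The sample size and the analysis rule may not fit each other. The size uses the whole 0.05 for the chronic contrast. The analysis rule, read plainly, could require 0.025 for each of the two contrasts.

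What is at stake is how a p-value between 0.025 and 0.05 is read. It would be positive if the rule stops at post hoc tests and negative if the rule reaches the two aims. If the planned effects are true, the chronic p-value lands in that gap in about 10% of trials (81.5% - 71.6% = 9.9 percentage points). In those trials, whether sex is declared to influence the chronic response could be settled after the data are seen.

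**Working it through.** **Inputs from the plan.** Alpha 0.05; power 80%; effect sizes for the sex difference of 1.57 (acute) and 1.28 (chronic); 11 per sex.

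**Assumptions.** Tests are two-sided (the plan does not say, but one-sided 0.05 would need only 9 per sex). Each contrast is a two-sample t-test on a change score. The correlation between the acute and chronic contrasts is not given, so a range of 0 to 0.9 is used.

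**Step 1: reproduce the stated size.** Power = P(|T| > t(1 - α/2, 2n - 2)), where T is noncentral t with 2n - 2 degrees of freedom and noncentrality ES × √(n/2).

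- Chronic, n = 10: noncentrality 1.28 × √5 = 2.86; power 77.2%.
- Chronic, n = 11: noncentrality 1.28 × √5.5 = 3.00, critical value 2.086; power 81.5%. So 11 is the smallest n that reaches 80%.
- Acute: 8 per sex is enough. At n = 11 the noncentrality is 1.57 × √5.5 = 3.68 and power is 93.8%.

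The stated 11 is therefore set by the chronic contrast at the full 0.05.

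**Step 2: Bonferroni covers the two contrasts.** Alpha is 0.05/2 = 0.025 each, and the critical value on 20 degrees of freedom rises to 2.423.

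- Chronic power at 11 per sex: 71.6%.
- Acute power at 11 per sex: 88.6%.
- Restoring 80% for the chronic contrast needs 13 per sex, or 26 completers.

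**Step 3: Bonferroni does not cover them, and either alone counts as support.** If the contrasts are independent, the chance of at least one false claim is 1 - 0.95² = 9.75%. For correlated contrasts (bivariate normal calculation, or simulation with 11 per sex where marked):

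| Correlation | Chance of at least one false claim |
|---|---|
| 0 | 9.75% |
| 0.3 | 9.5% |
| 0.5 | 9.1% |
| 0.7 | 8.3% |
| 0.8 | 7.9% (simulated) |
| 0.9 | 7.0% |

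**Step 4: both must succeed.** Each is tested at 0.05 with no split. Joint power is 0.815 × 0.938 = 76.4% if independent, about 78% at correlation 0.5 and about 81% at 0.9 (simulated).

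**Step 5: two procedures that control the error with the same 22 people.**

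- *Holm.* The smaller p-value is tested at 0.025; if it passes, the other is tested at 0.05. Simulated chronic power is 80.5% at correlation 0 and 79.8% at 0.5. Acute power is about 92% at correlation 0, 91% at 0.5 and 89% at 0.9.
- *Fixed sequence, chronic first.* Chronic power stays at 81.5%. The acute claim now needs both tests to pass, so its power equals the joint power in Step 4: about 76% at correlation 0 and 78-79% at 0.5, down from 93.8%.

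**The case against.** The strongest reply has four parts.

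1. *The plan never calls the contrasts co-primary.* That is true. It has two numbered aims and one primary outcome, and treating separate aims as separate families is a position some would defend. But the primary objective names both contrasts without ranking them, one sentence sizes both, and nothing demotes either. The plan does not adopt the separate-families position either.
2. *A multiplicity rule already exists.* The Bonferroni sentence mentions multiple tests alongside post hoc ones, so it can be read as reaching the two contrasts. On that reading the error is controlled. The sample size then misses its own power target.
3. *The overarching hypothesis speaks of acute and chronic responsiveness together.* If both must succeed, there is no inflation and no split. This stands as a third reading, so a reader should not infer that the only choices are a doubled error rate or lost power. The plan does not state this rule, and at correlations up to 0.5 it also falls a little short of 80%.
4. *Correlation softens the inflation.* This stands. The plan expects that "acute endothelial responses to exercise will be predictive of chronic endothelial adaptations". A rate of 9-10% applies only up to a correlation of about 0.5; at 0.8 to 0.9 it is 7-8%.

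It is also fair to say that the planned ANOVAs are wider than a t-test on one change score: three visits for Aim 1, and four time points in two training states for Aim 2. That means an order or a correction settles little until the contrasts themselves are named.

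**Conclusion.** The concern holds in a limited form. The stated 11 per sex is correct for the chronic contrast at an undivided two-sided 0.05, and the plan's own Bonferroni sentence, if it reaches the two contrasts, takes chronic power from 81.5% to 71.6%. If it does not reach them and either contrast suffices, the study-wise error is roughly 7-10%, depending on a correlation the plan does not give. If both must succeed, error is controlled and joint power is about 76-81% across correlations of 0 to 0.9.

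A reader might infer that the trial is certainly underpowered, or that its error rate is certainly near 10%. The documents support neither, because they do not fix the family or the success rule. Nor do they show that 11 per sex must be raised: a suitable procedure keeps it. The figures assume the preliminary effect sizes are right, all 22 people are analysed, and a two-sample t-test on change scores stands in for the ANOVA interaction.

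**What to change.** Amend the Statistical analyses paragraph in three ways:

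1. Name one chronic and one acute sex-by-time contrast as the two primary tests. For the acute contrast, give the post-exercise time point and whether it is taken in the untrained or trained state.
2. Apply Holm to these two at a study-wise two-sided 0.05.
3. Limit the Bonferroni sentence to post hoc tests within each ANOVA.

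The cost is a few sentences and no extra participants. Chronic power goes from 81.5% to about 80%, and acute power from 93.8% to 89-92%.

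A chronic-first fixed sequence, which follows the order of the aims, is an acceptable alternative only if its price is written down: acute power of about 76-79% at correlations of 0 to 0.5, with the acute result exploratory whenever the chronic test fails.
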